- b. aspartate or alanine aminotransferase (AST or ALT) > 3 × ULN;
- c. alkaline phosphatase > 2.5 × ULN.

23. Creatinine clearance < 30 mL/min, calculated using the Cockcroft-Gault formula (see [Section 4.5.8](#)).

24. Electrocardiogram (ECG) with a QT interval corrected according to Fridericia's formula (QTcF) > 500 msec at the Screening.

Other Exclusions:

25. Inability to return for follow-up visits or obtain follow-up data required to assess study therapy, or presence of other reasons for anticipated non-compliance to therapy or procedures, in the opinion of the investigator.

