4.5.8 Laboratory, Biomarker, and Other Biological Samples

All samples for laboratory tests (hematology, blood chemistry, serologic tests) will be analyzed in the study site's local laboratory.

Blood samples should be obtained in fasted patients and handled appropriately. The following parameters will be utilized in the study:

- hematology (plasma): white blood cells (WBC) count, red blood cells (RBC) count, hemoglobin, hematocrit, platelet count, (relative) differential WBC count (neutrophils, eosinophils, basophils, monocytes, lymphocytes);
- blood chemistry panel (serum or plasma): albumin, alkaline phosphatase (AP), ALT, AST, direct bilirubin, total bilirubin, total protein, albumin, cholesterol, creatine kinase (CK), creatinine, triglycerides, gamma-glutamyl transferase

Pirfenidone—F. Hoffmann-La Roche Ltd

(GGT), glucose, lactic dehydrogenase (LDH), calcium, phosphorus, magnesium, potassium, sodium, urea nitrogen, uric acid;

- serologic tests (at screening only, exclusion tests): rheumatoid factor, anticyclic citrullinated peptide and antinuclear antibody titer.

Creatinine clearance

Creatinine clearance should be assessed at the Screening for eligibility confirmation using the following formula by Cockcroft-Gault (Cockcroft DW et al, 1976):

For serum creatinine concentration in mg/dL:

$$\text{CrCl (mL/min)} = (140 - \text{age (years)}) \times \text{weight (kg)} \times 1.0 / 72 \times \text{serum creatinine (mg/dL)}$$

For serum creatinine concentration in $\mu\text{mol/L}$:

$$\text{CrCl (mL/min)} = (140 - \text{age (years)}) \times \text{weight (kg)} \times 1.0 / 0.81 \times \text{serum creatinine (\mu mol/L)}$$

Pregnancy test

All women of childbearing potential will have a urine pregnancy test at the Screening and on Day 1 before start of treatment. Only women with negative pregnancy test will be included in the study. Urine pregnancy tests will be performed repeatedly at specified subsequent visits as scheduled in the [Appendix 1](#).

If a urine pregnancy test is positive, it must be confirmed by a serum pregnancy test. Women with confirmed positive pregnancy test should be immediately withdrawn from the study treatment (see [Section 5.4.3](#)). Urine pregnancy test will be performed by the investigator using test-strips with least sensitivity to human chorionic gonadotropin (hCG) of 10 mLU/mL.

The investigator can perform clinical laboratory assessments more frequently, if it is clinically indicated.

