5.1.2 Management of Patients Who Experience Specific Adverse Events

Guidelines for management of specific adverse events are outlined in Table 3.

Table 3 Guidelines for Management of Patients Who Experience Specific Adverse Events

Event	Action to Be Taken
Gastrointestinal adverse events (nausea, vomiting, diarrhoea, dyspepsia)	
Confirm that the study drug is administered with food.
 
If symptoms persist when the drug is taken with food, the dose of pirfenidone should be reduced to 1-2 capsules (267-534 mg) 2-3 times/ day with food.
 
If symptoms resolve, the dose can be re-escalated to the recommended daily dose as tolerated.
 
If symptoms continue, treatment should be interrupted for 1-2 weeks to allow symptoms to resolve.
 
If symptoms continue after temporal interruption, treatment should be permanently discontinued.

Skin-related adverse events (photosensitivity reaction and rash)	
Mild to moderate photosensitivity reaction or rash - the dose of pirfenidone should be reduced to 801 mg (3 capsules) per day (267 mg (1 capsule) 3 times a day). Confirm that the patient uses a sunblock daily and avoids sun exposure.
 
If the rash persists after 7 days, pirfenidone should be discontinued for 15 days, with re-escalation to the recommended daily dose in the same manner as the dose escalation period.
 
Severe photosensitivity reaction or rash - treatment should be interrupted and medical advice is sought.
 
If the rash has resolved, pirfenidone may be re-introduced and re-escalated up to the recommended daily dose at the discretion of the investigator.

Elevations of ALT and AST	
ALT/ AST elevation > 3 to $\leq 5 \times$ ULN - confounding medicinal products should be discontinued, other causes excluded, and the patient monitored closely. If clinically appropriate, the dose of pirfenidone should be reduced or interrupted. Once liver function tests are within normal limits the dose may be re-escalated to the recommended daily dose if tolerated.
 
ALT/ AST elevation to $\leq 5 \times$ ULN accompanied by symptoms or hyperbilirubinaemia ($> 2 \times$ ULN) - treatment should be permanently discontinued.
 
ALT/ AST elevation to $> 5 \times$ ULN - treatment should be permanently discontinued.

Table 3 Guidelines for Management of Patients Who Experience Specific Adverse Events (cont.)

Event	Action to Be Taken

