6.5 SAFETY ANALYSES

The *Treated set* will be used for the analysis of the safety and tolerability data.

Study treatment is defined as pirfenidone 2403 mg/d administered in divided doses TID with food. Study treatment will be titrated over 14 days to the full dose of 9 capsules per day (three 267-mg capsules taken orally TID with food). Patients will remain on a stable maintenance dose for the duration of the treatment period unless the dose is reduced to manage an AE or titrated again when restarting study treatment after a 28-day or greater interruption in treatment.

AEs will be reported on a per-subject basis, *i.e.* counting subjects rather than events. Only treatment emergent AEs will be reported. In the listings, however, all occurrences of the AEs will be presented.

Treatment emergent AEs will be summarized per primary *SOC* and *PT*. Severity and drug-event relationship of treatment emergent AEs will be summarized separately.

Vital signs, including changes from baseline will be listed *and* summarized with descriptive statistics (mean, *SD*, median, minimum and maximum) for each measurement time point. Out-of-range values with assessment of clinical significance will be provided in frequency tables.

Results of ECG, including changes from baseline will be listed *and* summarized with descriptive statistics (mean, *SD*, median, minimum and maximum) for each measurement time point. Out-of-range values with assessment of clinical significance will be provided in frequency tables.

Pirfenidone—F. Hoffmann-La Roche Ltd

140/Protocol ML39355, Version 2 dated 09-Jun-2018

Laboratory variables, including changes from baseline will be listed and summarized with descriptive statistics (mean, *SD*, median, minimum and maximum) for each measurement time point. Additionally, shift tables summarizing the frequencies of patients below, within, and above the normal ranges at each time point will be provided.

Results of physical examinations will be summarized in corresponding frequency table and listing.

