6.5. Multi-center Studies

Data from all centers will be merged and analyzed as one population for all study endpoints.

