9.4. Clinical Laboratory Evaluations

eCRF form: “HEMATOLOGY”, “SERUM CHEMISTRY”.

Clinical laboratory evaluations as scheduled in the Table 1 include the following parameters:

- hematology (plasma): white blood cells (WBC) count, red blood cells (RBC) count, hemoglobin, hematocrit, platelet count, (relative) differential WBC count (neutrophils, eosinophils, basophils, monocytes, lymphocytes);
- blood chemistry panel (serum or plasma): albumin, alkaline phosphatase (AP), ALT, AST, direct bilirubin, total bilirubin, total protein, cholesterol, creatine kinase (CK), creatinine, triglycerides, gamma-glutamyl transferase (GGT), glucose, lactic dehydrogenase (LDH), calcium, phosphorus, magnesium, potassium, sodium, urea nitrogen, uric acid;

Creatinine clearance should be assessed at the Screening for eligibility confirmation using the following formula by Cockcroft-Gault (Cockcroft DW et al, 1976):

For serum creatinine concentration in mg/dL:

ML39355_STATISTICAL ANALYSIS PLAN_Final 2.0_17 June 2020

$$\text{CrCl (mL/min)} = (140 - \text{age (years)}) \times \text{weight (kg)} \times 1.0 / 72 \times \text{serum creatinine (mg/dL)}$$

For serum creatinine concentration in $\mu\text{mol/L}$:

$$\text{CrCl (mL/min)} = (140 - \text{age (years)}) \times \text{weight (kg)} \times 1.0 / 0.81 \times \text{serum creatinine } (\mu\text{mol/L})$$

For laboratory parameters the following tables will be presented according to section 7:

- descriptive statistics of measured values and changes from baseline (including creatinine clearance);
- shift tables based on comparison with normal range (Lower/Normal/Higher);
- frequency tables for Out of range: No/Yes clinically significant (Yes CS) / Yes non-clinically significant (Yes NCS) for laboratory parameters.

All laboratory data will be listed.

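### No planned summary table counts patients whose ALT or AST crosses the protocol's own 3x and 5x ULN thresholds, or sets transaminases against bilirubin

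*SAP*

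**What the plan says.** SAP 9.4 plans three kinds of laboratory table, all by visit:

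- "descriptive statistics of measured values and changes from baseline (including creatinine clearance"), which for chemistry is Table 3.17, in U/L for the transaminases, with mean, SD, median, minimum and maximum;
- "shift tables based on comparison with normal range (Lower/Normal/Higher"), which is Table 3.19;
- out-of-range frequencies split into clinically significant and not clinically significant, which is Table 3.21.

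The shift table follows Protocol 6.5, under which "shift tables summarizing the frequencies of patients below, within, and above the normal ranges at each time point will be provided".

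Other passages bear on how these tables read:

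- **Entry.** Protocol 4.1.2, criterion 22b, excludes "aspartate or alanine aminotransferase (AST or ALT) > 3 × ULN" at Screening, so a patient at 2.5x ULN is eligible. Criterion 22a excludes any total bilirubin above ULN.
- **Action levels.** Protocol 5.1.2, Table 3, has separate rows of action for ALT/AST >3 to ≤5x ULN, for elevations up to 5x ULN "accompanied by symptoms or hyperbilirubinaemia" (bilirubin >2x ULN), and for >5x ULN.
- **Combined criterion.** Protocol 5.3.5.6 requires ALT or AST >3x ULN with total bilirubin >2x ULN, or with clinical jaundice, to be reported as an adverse event and sent to the Sponsor immediately.
- **Laboratories.** Under Protocol 4.5.8, samples "will be analyzed in the study site's local laboratory". SAP 6.5 adds: "Data from all centers will be merged and analyzed as one population for all study endpoints".

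**The concern.** Protocol 5.1.1.3 names ALT and AST elevations above 3x ULN as a reported effect of pirfenidone, and change in laboratory parameters is a stated safety endpoint. A reader of the study report will want to know how many patients exceeded 3x and 5x ULN, and how many did so with raised bilirubin. The planned laboratory tables do not give those counts.

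The Low/Normal/High rule has a single cut at ULN, so it does not register movement within the abnormal range. The numeric table does not fill the gap, because raw U/L from several laboratories with their own reference limits cannot be read as multiples of ULN. What is at stake is a clear count for a named risk in a study of about 60 patients, where a few cases could make up all the information there is.

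**Working it through.** The plan states no figure on this point, so the check is a classification, followed by a trace of where an elevated value would be reported.

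**Step 1: classify values under both rules.** Inputs are the SAP 9.4 categories and bands cut at the 3x and 5x ULN levels of Protocol Table 3. Values are multiples of ULN.

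| Baseline | Post-baseline | SAP shift table | Bands at protocol levels |
|---|---|---|---|
| 0.8 | 2.5 | Normal to High | ≤1 to >1-3 |
| 0.8 | 4 | Normal to High | ≤1 to >3-5 |
| 0.8 | 8 | Normal to High | ≤1 to >5 |
| 2.5 | 4 | High to High | >1-3 to >3-5 |
| 2.5 | 8 | High to High | >1-3 to >5 |

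The first three rows share one shift-table cell, as would a rise to only 1.1x ULN. The last two rows lie on the diagonal and read as no shift.

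**Step 2: the descriptive table.** One patient's contribution to the mean change is (post − baseline)/N. With N = 60:

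- 2.5x to 4x: (4 − 2.5)/60 = 0.025x ULN
- 2.5x to 8x: (8 − 2.5)/60 = 0.09x ULN

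Neither is recognisable in a mean. The maximum would show an extreme value, but in U/L pooled over local laboratories, so it cannot be placed against 3x or 5x ULN.

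**Step 3: the out-of-range table.** Its split rests on the investigator's judgement of significance and has no ULN cut.

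**Step 4: timing.** All three tables are by visit. The hematology shells (3.16, 3.18, 3.20), on which the chemistry tables are modelled, go from Week 8 to Week 16, although Protocol 4.5.13.6 and Appendix 1 schedule chemistry at Week 12. Protocol 4.5.8 also allows extra tests when clinically indicated, and the shells list only named visits. A peak at Week 12 or at an unscheduled test can therefore be missing from every laboratory table.

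**Step 5: the adverse event route.** Protocol 5.3.5.4 makes a laboratory result an adverse event if it is symptomatic, changes study treatment, leads to an intervention or a change in concomitant therapy, or is judged clinically significant.

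| Situation | Reaches adverse event tables? |
|---|---|
| ALT/AST >5x ULN, handled per Table 3 | Yes: study treatment changes, so TEAE Tables 3.3.x, 3.7.x (CTCAE grade) and 3.11.x (discontinuation) |
| ALT/AST >3x with bilirubin >2x ULN or jaundice | Yes: mandatory report as SAE or AESI |
| ALT/AST >3 to ≤5x with dose change, interruption or change in concomitant drug | Yes |
| ALT/AST >3 to ≤5x, asymptomatic, monitored only, not judged significant | Not required |

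The last row is the gap. Table 3 makes a dose reduction or interruption in that band conditional on clinical appropriateness, so monitoring alone is possible. Such a patient is identifiable only from Listing 31. Protocol 5.2.3.2 directs the IDMC's attention to liver enzyme increases reported as adverse events, which does not cover this patient either.

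**The case against.** The strongest reply is that liver safety is reported by several routes and that the SAP does what the protocol asks. Much of this stands.

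- Protocol 6.5 prescribes below/within/above shift tables, so SAP 9.4 is not a departure.
- A reader might infer that the shift table and pooled means are all there is. They are not: the clinical-significance table exists, and Table 3.17 gives median, minimum and maximum.
- A reader might infer that a rise from 2.5x to 8x ULN would go unseen. It would show no shift, but under Table 3 and Protocol 5.3.5.4 that patient should appear among TEAEs leading to discontinuation, and in Tables 3.7.x with a CTCAE grade. The adverse event tables therefore do carry severity, although the AESI tables do not. The documents do not give the CTCAE laboratory cut-offs.
- A reader might infer that the thresholds cannot be recovered at all. Listing 31 shows each result with its reference limits, so they can be worked out patient by patient.
- High to High needs a baseline already above ULN, and the documents do not say how many patients will have one. For bilirubin it hardly arises, given criterion 22a.
- The documents do not rank liver injury above other risks and give no rate for it. Protocol 1.3.2 puts gastrointestinal and skin events among the most commonly reported.

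What remains is that a listing is not a count. To answer how many patients exceeded 3x ULN, a reader would have to divide each result by its own upper limit by hand.

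**Conclusion.** The point holds in a limited form. No summary table counts patients with ALT or AST above 3x or 5x ULN, and none sets transaminases against bilirubin. The part not backed up by the adverse event tables is the isolated >3 to ≤5x ULN elevation that is only monitored.

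The size is structural: within the abnormal range the shift table cannot register a change. Each affected patient is 1/60 = 1.7% of the planned sample. No expected number can be given, because the documents state neither the rate of such elevations nor the share of patients entering above ULN.

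The conclusion assumes that Table 3 and Protocol 5.3.5.4 are followed, and that chemistry is run locally as Protocol 4.5.8 says. Protocol 7.1 mentions central laboratory data. If that were what happened, the objection to pooled U/L would weaken, but the missing thresholds and the missing worst value would remain. This is an inexpensive improvement to reporting and does not affect the efficacy analysis.

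**What to change.** In SAP 9.4, add one table on the Treated set, produced for the treatment period and for the rollover period as SAP 9.2 defines them:

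- worst post-baseline ALT and AST, each divided by the reporting laboratory's ULN, in categories ≤1, >1-3, >3-5 and >5;
- worst post-baseline total bilirubin, likewise divided, in categories ≤1, >1-2 and >2;
- each cross-tabulated by baseline category;
- the number and percentage of patients with ALT or AST >3x ULN together with bilirubin >2x ULN or reported clinical jaundice.

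State that Week 12 and unscheduled results count towards the worst value, and add Week 12 to the existing laboratory shells. The cut points are those already in Protocol 5.1.2 and 5.3.5.6. Alkaline phosphatase needs no such bands, because the protocol sets no on-treatment level for it. Reconcile Protocol 7.1 with 4.5.8 on central versus local laboratories, so that the ULN used is unambiguous.

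The cost is one extra table shell and its programming. Results and limits are already in Listing 31, no tests are added, and no clinical rule changes. SAP section 2 allows revision before database soft lock.

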9.5. Other Safety Measures

eCRF form: “VITAL SIGNS”, “ECG”, “PHYSICAL EXAMINATION”.

Vital signs

Vital signs (respiratory rate (breaths/ minute), pulse rate (beats/ minute), and systolic and diastolic blood pressure (mmHg), and axillary temperature ($^{\circ}\text{C}$)), body weight (kg) and body height (cm) results will be presented in accordance with section 7.

Vital signs results will be presented by visit of assessment as scheduled in the Table 1. Body height will be assessed only at screening.

Vital signs and body weight results will be presented as the following outputs:

- descriptive statistics for measured values and changes from baseline (vital signs, body weight, BMI);
- frequency tables for Out of range: No/Yes clinically significant (Yes CS) / Yes non-clinically significant (Yes NCS) (vital signs).

All data will be listed.

ECG

A 12-lead electrocardiogram (ECG) results will be represented in accordance with section 7 by visit of assessment as scheduled in the Table 1 as the following outputs:

- shift table by post baseline visit compared to baseline for Normal/Abnormal clinically significant (Abnormal CS) / Abnormal non-clinically significant (Abnormal NCS) evaluation for General assessment

ML39355_STATISTICAL ANALYSIS PLAN_Final 2.0_17 June 2020

- descriptive statistics of ECG parameters and their changes from baseline (Heart rate, beats/min; QT interval, ms; QTC-F interval, ms).
- frequency table for Out of range: No/Yes clinically significant (Yes CS) / Yes non-clinically significant (Yes NCS) for ECG parameters.

All ECG data will be listed.

Physical examinations

Complete physical examination is performed at the Screening only (head, eyes, ears, nose, and throat, and the cardiovascular, dermatological, musculoskeletal, respiratory, gastrointestinal, genitourinary, and neurological systems). At subsequent visits, only limited, symptom-directed physical examinations should be performed.

Physical examination results as scheduled in the Table 1 will be presented in accordance with section 7 by visit of assessment as the following output:

- frequency table for Normal/Abnormal clinically significant (Abnormal CS) / Abnormal non-clinically significant (Abnormal NCS) evaluation.

All physical examination data will be listed.

10. Pharmacokinetics

Not Applicable.

11. Other Analyses

Not Applicable.

12. Reporting Conventions

Not Applicable.

13. Technical Details

Statistical analysis will be performed using SAS 9.4.

One (final) statistical analysis report will be prepared in the Microsoft Office Word (.docx) format after the end of data collection and database lock. The results of statistical analysis will be presented in the form of tables, figures and listings in English.

14. Summary of Changes to the Protocol

ML39355_STATISTICAL ANALYSIS PLAN_Final 2.0_17 June 2020

The analyses methods in this SAP are fully consistent with the clinical study Protocol.

ML39355_STATISTICAL ANALYSIS PLAN_Final 2.0_17 June 2020

15. References

- 1) Committee for Proprietary Medicinal Products (CPMP). International Conference on Harmonisation (ICH) Topic E9: Note for Guidance on Statistical Principles for Clinical Trials; September 1998.
- 2) DataMatrix_SOP_STAT001_Statistical Principles_ver.3.0_June 2019.
- 3) DataMatrix_SOP_STAT002_Statistical Analysis Plan Development_ver.2.0_July 2017.
- 4) DataMatrix_SOP_DM010_Dictionary Management and Data Coding_ver.2.0_August 2015.
- 7) ML39355 Study Results Posting Requirements.

ML39355_STATISTICAL ANALYSIS PLAN_Final 2.0_17 June 2020

16. Listing of Tables, Listings and Figures

16.1. Tables

Patients Disposition

- Table 1.1 Patients disposition (All Enrolled patients)
- Table 1.2 Violation of eligibility criteria (Screening Failures)
- Table 1.3 Analysis populations (Allocated to treatment set)
- Table 1.4 Study visits

Protocol Deviations

- Table 1.5 Protocol deviations / violations (Allocated to treatment set)

Demographic and Anthropometric characteristics

- Table 1.6 Demographic characteristics (TS)
- Table 1.7 Anthropometric characteristics (TS)

Baseline Variables

- Table 1.8 Surgical lung biopsy (TS)
- Table 1.9 HRCT for patient eligibility confirmation (TS)
- Table 1.10 Carbon monoxide diffusing capacity (DLCO) (TS)
- Table 1.11 Pre- and post-bronchodilator spirometry parameters at screening (TS)
- Table 1.12 Serologic tests (TS)
- Table 1.13 GAP assessment (TS)
- Table 1.14 Review transbronchial lung biopsy/BAL (TS)

Medical history

- Table 1.15 Prior medical/surgical conditions/diagnoses (TS)
- Table 1.16 Concurrent medical/surgical conditions/diagnoses (TS)
- Table 1.17 History of idiopathic pulmonary fibrosis (TS)

Prior and concomitant medications

- Table 1.18 Prior medications (TS)
- Table 1.19 Concomitant medications (TS)
- Table 1.20 Concomitant medications during rollover study (TS)

Efficacy Analyses

- Table 2.1 Descriptive statistics for FVC by visit (FAS)
- Table 2.2 Primary efficacy endpoint (FAS)
- Table 2.3 Primary efficacy endpoint: categorical results (FAS)
- Table 2.4 Primary efficacy endpoint by pattern type (CSS)
- Table 2.5 6-Minute Walk Test (FAS)
- Table 2.6 Change in 6MWT distance at Week 26 by category (FAS)
- Table 2.7 Borg scale (FAS)
- Table 2.8 EQ-5D-5L. Descriptive statistics (FAS)
- Table 2.9 Change in EQ-5D-5L. Mobility (FAS)
- Table 2.10 Change in EQ-5D-5L. Self-Care (FAS)
- Table 2.11 Change in EQ-5D-5L. Usual Activities (FAS)
- Table 2.12 Change in EQ-5D-5L. Pain/Discomfort (FAS)
- Table 2.13 Change in EQ-5D-5L. Anxiety/Depression (FAS)
- Table 2.14 EQ-5D-5L. VAS and Index score (FAS)
- Table 2.15 HRCT. HRCT fibrosis score (FAS)
- Table 2.16 HRCT. Lung opacity score (FAS)
- Table 2.17 Exacerbation cases during treatment period (FAS)
- Table 2.18 Exacerbation cases during rollover study (FAS, patients continuing in the rollover study)
- Table 2.19 Exacerbation cases during whole study period (FAS, patients continuing in the rollover study)

Safety Analyses

- Table 3.1 Duration of exposure (TS)
- Table 3.2 Total number of capsules taken (TS)
- Table 3.3.1 Treatment-emergent adverse events during treatment period (TS)
- Table 3.3.2 Treatment-emergent adverse events during rollover study (TS, patients continuing in the rollover study)
- Table 3.3.3 Treatment-emergent adverse events during whole study period (TS)
- Table 3.4.1 Treatment-emergent adverse events related to the study drug during treatment period (TS)
- Table 3.4.2 Treatment-emergent adverse events related to the study drug during rollover study (TS, patients continuing in the rollover study)

ML39355_STATISTICAL ANALYSIS PLAN_Final 2.0_17 June 2020

Table 3.4.3 Treatment-emergent adverse events related to the study drug during whole study period (TS)

Table 3.5.1 Serious treatment-emergent adverse events during treatment period (TS)

Table 3.5.2 Serious treatment-emergent adverse events during rollover study (TS, patients continuing in the rollover study)

Table 3.5.3 Serious treatment-emergent adverse events during whole study period (TS)

Table 3.6.1 Serious treatment-emergent adverse events related to the study drug during treatment period (TS)

Table 3.6.2 Serious treatment-emergent adverse events related to the study drug during rollover study (TS, patients continuing in the rollover study)

Table 3.6.3 Serious treatment-emergent adverse events related to the study drug during whole study period (TS)

Table 3.7.1 Treatment-emergent adverse events during treatment period by maximum severity (TS)

Table 3.7.2 Treatment-emergent adverse events during rollover study by maximum severity (TS, patients continuing in the rollover study)

Table 3.7.3 Treatment-emergent adverse events during whole study period by maximum severity (TS)

Table 3.8.1 Treatment-emergent adverse events related to the study drug during treatment period by maximum severity (TS)

Table 3.8.2 Treatment-emergent adverse events related to the study drug during rollover study by maximum severity (TS, patients continuing in the rollover study)

Table 3.8.3 Treatment-emergent adverse events related to the study drug during whole study period by maximum severity (TS)

Table 3.9.1 Treatment-emergent adverse events of special interest during treatment period (TS)

Table 3.9.2 Treatment-emergent adverse events of special interest during rollover study (TS, patients continuing in the rollover study)

Table 3.9.3 Treatment-emergent adverse events of special interest during whole study period (TS)

Table 3.10.1 Treatment-emergent adverse events leading to death during treatment period (TS)

Table 3.10.2 Treatment-emergent adverse events leading to death during rollover study (TS, patients continuing in the rollover study)

Table 3.10.3 Treatment-emergent adverse events leading to death during whole study period (TS)

Table 3.11.1 Treatment-emergent adverse events leading to discontinuation of study drug during treatment period (TS)

Table 3.11.2 Treatment-emergent adverse events leading to discontinuation of study drug during rollover study (TS, patients continuing in the rollover study)

Table 3.11.3 Treatment-emergent adverse events leading to discontinuation of study drug during whole study period (TS)

Table 3.12.1 Treatment-emergent adverse events related to study drug and leading to death during treatment period (TS)

Table 3.12.2 Treatment-emergent adverse events related to study drug and leading to death during rollover study (TS, patients continuing in the rollover study)

Table 3.12.3 Treatment-emergent adverse events related to study drug and leading to death during whole study period (TS)

Table 3.13.1 Non-serious treatment-emergent adverse events occurred at a frequency of $\geq 5\%$ during treatment period (TS)

Table 3.13.1 Non-serious treatment-emergent adverse events occurred at a frequency of $\geq 5\%$ during rollover study (TS, patients continuing in the rollover study)

Table 3.13.1 Non-serious treatment-emergent adverse events occurred at a frequency of $\geq 5\%$ during whole study period (TS)

Table 3.14 Deaths

Table 3.15 Urine pregnancy test (TS, women of childbearing potential)

Table 3.16 Hematology. Descriptive statistics (TS)

Table 3.17 Blood chemistry. Descriptive statistics (TS)

Table 3.18 Hematology. Shift table (TS)

Table 3.19 Blood chemistry. Shift table (TS)

Table 3.20 Hematology. Out of range. Frequency table

Table 3.21 Blood chemistry. Out of range. Frequency table (TS)

ML39355_STATISTICAL ANALYSIS PLAN_Final 2.0_17 June 2020

Table 3.22 Vital signs. Descriptive statistics (TS)
Table 3.23 Vital signs. Out of range. Frequency table (TS)
Table 3.24 Weight. Descriptive statistics (TS)
Table 3.25 ECG. Descriptive statistics (TS)
Table 3.26 ECG. Out of range and General Assessment. Frequency table (TS)
Table 3.27 Physical examinations. Frequency table (TS)

ML39355_STATISTICAL ANALYSIS PLAN_Final 2.0_17 June 2020
Patients Disposition

 F. Hoffmann-La Roche Ltd
 ML39355

Table 1.1 Patients disposition

All Enrolled patients

Page X of X

	Total (N = XX) n (%)
Patients who signed the Informed Consent Form	XX
Screening Failures	XX
Reasons for premature discontinuation	XX
Patient request or withdrawal of consent	XX
Presence or development of Inclusion/Exclusion criterion (-a)	XX
Allocated to treatment	xx
Treated during the treatment period	XX (XX.X)
Patients continuing (treated) in the rollover study	XX (XX.X)
Completed	XX (XX.X)
Terminated Prematurely	XX (XX.X)
Reasons for premature discontinuation	
Pregnancy	XX (XX.X)
Unacceptable tolerability and personal safety profile (e.g. adverse events listed in Section 5.1.2 of Protocol, or serious adverse events related to study treatment)	XX (XX.X)
Patient request or withdrawal of consent	XX (XX.X)
Any medical condition that the investigator or Sponsor determines may jeopardize the patient's safety if he or she continues in the study	XX (XX.X)
Investigator or Sponsor determines it is in the best interest of the patient for other reasons	XX (XX.X)
Protocol deviation (at Sponsor's discretion) (e.g. refusal to follow study requirements)	XX (XX.X)
Termination of the whole study by the Sponsor	XX (XX.X)
Lung transplantation	XX (XX.X)
The incidence or severity of adverse events in this or other ongoing studies of pirfenidone indicates a potential health hazard to patients	XX (XX.X)
Patient enrollment is unsatisfactory	XX (XX.X)
Administrative and regulatory reasons	XX (XX.X)
Presence or development of Inclusion/Exclusion criterion (-a)	XX (XX.X)
Other	XX (XX.X)

ML39355_STATISTICAL ANALYSIS PLAN_Final 2.0_17 June 2020

Other reason 1	XX (XX.X)
Other reason 2	XX (XX.X)
...	XX (XX.X)

N: the number of patients who signed the Informed Consent Form.

n: the number of patients within a specific category. Percentages are calculated based on number of patients Allocated to Treatment.

Path to the program code, date and time of output

Data extracted: DD.MM.YYYY

ML39355_STATISTICAL ANALYSIS PLAN_Final 2.0_17 June 2020

F. Hoffmann-La Roche Ltd
ML39355

Table 1.2 Violation of eligibility criteria
Screening Failures
Page X of X

	Total (N = XX)
Patients with any violation of eligibility criteria	XX
Patients with any violation of inclusion criteria	XX
Inclusion criterion #1	XX
Inclusion criterion #2	XX
...	...
Patients with any violation of exclusion criteria	XX
Exclusion criterion #1	XX
Exclusion criterion #2	XX
...	...

N: the number of Screening Failures.

n: the number of patients within a specific category.

Path to the program code, date and time of output

Data extracted: DD.MM.YYYY

ML39355_STATISTICAL ANALYSIS PLAN_Final 2.0_17 June 2020

 F. Hoffmann-La Roche Ltd
 ML39355

Table 1.3 Analysis populations

 Allocated to treatment set
 Page X of X

	Total (N = XX) n (%)
Allocated to treatment	XX (100%)
Treated set (TS)	XX (XX.X)
Full analysis set (FAS)	XX (XX.X)
Completed case set (CCS)	XX (XX.X)

N: the number of patients in the Allocated to treatment set.

n: the number of patients within a specific category. Percentages are calculated as $(100 \times n/N)$.

Treated set: patients from 'Allocated to treatment' set, who received any dose of the study treatment.

Full analysis set: patients from 'Treated' set, who had data for at least one post-baseline assessment of any efficacy measurement.

Completed case set: patients from 'Full analysis' set, who provided FVC data at 26-week assessment.

Path to the program code, date and time of output

Data extracted: DD.MM.YYYY

ML39355_STATISTICAL ANALYSIS PLAN_Final 2.0_17 June 2020

 F. Hoffmann-La Roche Ltd
 ML39355

Table 1.4 Study visits
 Allocated to treatment set
 Page X of X

	Total (N = XX) n (%)	Within visit window n (%)
Treatment period		
Start of Treatment (Day 1)	XX (XX.X)	N/A
Week 1 Telephone Assessment (+/- 1 day)	XX (XX.X)	XX (XX.X)
Week 2 (+/- 2 days)	XX (XX.X)	XX (XX.X)
Week 4 (+/- 2 days)	XX (XX.X)	XX (XX.X)
Week 8 (+/- 2 days)	XX (XX.X)	XX (XX.X)
Week 12 (+/- 2 days)	XX (XX.X)	XX (XX.X)
Week 16 (+/- 1 week)	XX (XX.X)	XX (XX.X)
Week 20 (+/- 1 week)	XX (XX.X)	XX (XX.X)
1st day at Week 26 (+/- 1 week)	XX (XX.X)	XX (XX.X)
2nd day at Week 26 (+/- 1 week)	XX (XX.X)	XX (XX.X)
Follow-up Visit (14-28 days after last dosing)	XX (XX.X)	XX (XX.X)
Long Term Follow-Up/Rollover Study		
Week 39 (+/- 2 weeks)	XX (XX.X)	XX (XX.X)
Week 52 (+/- 2 weeks)	XX (XX.X)	XX (XX.X)

N: the number of patients in the Allocated to treatment set.

n: the number of patients within a specific category. Percentages are calculated as (100 x n/N).

Path to the program code, date and time of output

Data extracted: DD.MM.YYYY

ML39355_STATISTICAL ANALYSIS PLAN_Final 2.0_17 June 2020
Protocol Deviations

 F. Hoffmann-La Roche Ltd
 ML39355

Table 1.5 Protocol deviations / violations

Allocated to treatment set

Page X of X

	Total (N = XX)
	n (%)
Patients with at least one protocol deviation	XX (XX.X)

N: the number of patients in the Allocated to treatment set.

 n: the number of patients with at least one protocol deviation. Percentages are calculated as $(100 \times n/N)$.

Path to the program code, date and time of output

Data extracted: DD.MM.YYYY

ML39355_STATISTICAL ANALYSIS PLAN_Final 2.0_17 June 2020

Demographic and Anthropometric characteristics

F. Hoffmann-La Roche Ltd
ML39355

Table 1.6 Demographic characteristics

Treated set
Page X of X

		Total (N = XX)
Age, years		
n		XX
Mean		XX.X
SD		XX.XX
Median		XX.X
Min		XX
Max		XX
Sex		
n		XX
Male	n (%)	XX (XX.X)
Female	n (%)	XX (XX.X)
Race		
n		XX
Caucasian	n (%)	XX (XX.X)
Asian	n (%)	XX (XX.X)
Black	n (%)	XX (XX.X)
Other	n (%)	XX (XX.X)
Other race 1	n (%)	XX (XX.X)
Other race 2	n (%)	XX (XX.X)
...
Ethnicity		
n		XX
Russian	n (%)	XX (XX.X)
Tatar	n (%)	XX (XX.X)
Ukrainian	n (%)	XX (XX.X)
Bashkir	n (%)	XX (XX.X)
Chuvash	n (%)	XX (XX.X)
Unknown	n (%)	XX (XX.X)
Other	n (%)	XX (XX.X)
Other ethnicity 1	n (%)	XX (XX.X)
Other ethnicity 2	n (%)	XX (XX.X)

ML39355_STATISTICAL ANALYSIS PLAN_Final 2.0_17 June 2020

N: the number of patients in the Treated set.

n: the number of valid measurements or the number of patients within a specific category. Percentages are calculated as $(100 \times n/N)$.

Path to the program code, date and time of output

Data extracted: DD.MM.YYYY

ML39355_STATISTICAL ANALYSIS PLAN_Final 2.0_17 June 2020

 F. Hoffmann-La Roche Ltd
 ML39355

Table 1.7 Anthropometric characteristics

 Treated set
 Page X of X

	Total (N = XX)
Height, cm	
N	XX
Mean	XX.X
SD	XX.XX
Median	XX.X
Min	XX
Max	XX
Weight, kg	
n	XX
Mean	XX.X
SD	XX.XX
Median	XX.X
Min	XX
Max	XX
Body Mass Index (BMI), kg/m ²	
n	XX
Mean	XX.XX
SD	XX.XXX
Median	XX.XX
Min	XX.X
Max	XX.X

N: the number of patients in the Treated set.
 n: the number of valid measurements.

Path to the program code, date and time of output

Data extracted: DD.MM.YYYY

ML39355_STATISTICAL ANALYSIS PLAN_Final 2.0_17 June 2020
Baseline Variables

F. Hoffmann-La Roche Ltd
 ML39355
Table 1.8 Surgical lung biopsy
 Treated set
 Page X of X

	Total (N = XX) n (%)
Assessment of regional specialist	
UIP Pattern	
n'	XX
Consistent UIP pattern	XX (XX.X)
Probable UIP pattern	XX (XX.X)
Possible UIP pattern	XX (XX.X)
Inconsistent/unclassified UIP pattern	XX (XX.X)
Assessment of central specialist	
UIP Pattern	
n'	XX
Consistent UIP pattern	XX (XX.X)
Probable UIP pattern	XX (XX.X)
Possible UIP pattern	XX (XX.X)
Inconsistent/unclassified UIP pattern	XX (XX.X)

N: the number of patients in the Treated set. n' - the number of valid observations.

n: the number of patients within a specific category. Percentages are based on the corresponding number of valid observations.

Path to the program code, date and time of output

Data extracted: DD.MM.YYYY

ML39355_STATISTICAL ANALYSIS PLAN_Final 2.0_17 June 2020

 F. Hoffmann-La Roche Ltd
 ML39355

Table 1.9 HRCT for patient eligibility confirmation

 Treated set
 Page X of X

	Total (N = XX) n (%)
Assessment of regional CT-specialist	
UIP Pattern	
n'	XX
Typical (apparent) UIP pattern	XX (XX.X)
Possible UIP Pattern	XX (XX.X)
Assessment of central CT-specialist (1)	
UIP Pattern	
n'	XX
Typical (apparent) UIP pattern	XX (XX.X)
Possible UIP Pattern	XX (XX.X)
Inconsistent with UIP Pattern	XX (XX.X)
Assessment of central CT-specialist (2)	
UIP Pattern	
n'	XX
Typical (apparent) UIP pattern	XX (XX.X)
Possible UIP Pattern	XX (XX.X)
Inconsistent with UIP Pattern	XX (XX.X)
Not Performed	XX (XX.X)

N: the number of patients in the Treated set. n' - the number of valid observations.

n: the number of patients within a specific category. Percentages are based on the corresponding number of valid observations.

Path to the program code, date and time of output

Data extracted: DD.MM.YYYY

ML39355_STATISTICAL ANALYSIS PLAN_Final 2.0_17 June 2020

 F. Hoffmann-La Roche Ltd
 ML39355

Table 1.10 Carbon monoxide diffusing capacity (DLCO)

 Treated set
 Page X of X

	Total (N = XX)
Predicted DLCO, %	
n	XX
Mean	XX.X
SD	XX.XX
Median	XX.X
Min	XX
Max	XX
Hb-corrected DLCO, %	
n	XX
Mean	XX.X
SD	XX.XX
Median	XX.X
Min	XX
Max	XX

N: the number of patients in the Treated set.
 n: the number of valid measurements.

Path to the program code, date and time of output

Data extracted: DD.MM.YYYY

ML39355_STATISTICAL ANALYSIS PLAN_Final 2.0_17 June 2020

 F. Hoffmann-La Roche Ltd
 ML39355

Table 1.11 Pre- and post-bronchodilator spirometry parameters at screening

 Treated set
 Page X of X

	Total (N = XX)
Pre-bronchodilator FEV1/FVC	
n	XX
Mean	XX.XX
SD	XX.XXX
Median	XX.XX
Min	XX.XX
Max	XX.XX
Post-bronchodilator FEV1/FVC	
n	XX
Mean	XX.XX
SD	XX.XXX
Median	XX.XX
Min	XX.XX
Max	XX.XX
...	

N: the number of patients in the Treated set.
 n: the number of valid measurements.

Path to the program code, date and time of output

Data extracted: DD.MM.YYYY

ML39355_STATISTICAL ANALYSIS PLAN_Final 2.0_17 June 2020
